### 7.2 Study design

[figure not shown]
The study will be conducted with an operational seamless design and will consist of 2 separate parts:

- Part 1 is a double-blind randomised placebo-controlled Phase 2b/3 study of 28 days of treatment that will include 3 arms (2 active doses: SENS-401 29 mg and SENS-401 43.5

mg and one placebo) with an 8-week follow-up. The primary end point of Part 1 will be the change in PTA at 28 days. At the conclusion of Part 1 treatment, the data for patients enrolled in this part of the study will be unblinded by the DMC for the purposes of analysis and the dose to be tested in the confirmatory part (Part 2) will be proposed by the DMC. Patients included in Part 1 will be completely separated from patients included in Part 2.

- Part 2 is a phase 3 study. This study will be a double blind randomised placebo controlled study of 28 days of treatment that will include 2 arms with an 8-week follow-up. SENS-401 dose, either 43.5 mg or 29 mg (selected after completion of Part 1) will be tested versus placebo.

Figure 1 - Operational Seamless Design

The principle of the operational design is to continue recruitment without interruption successively into Part 1, and Part 2, according to the following steps:

1. Patients will be randomised in 3 treatment arms in Part 1 (Placebo, SENS-401 29mg, SENS-401 43.5mg). A total of 111 subjects (37/treatment arm) will be randomised.
2. The Part 1 data will be unblinded after 111 patients have been randomised in Part 1 and have completed the end of treatment visit (28 days).
3. As soon as the dose is selected for Part 2, new patients will be randomised to 2 arms (SENS-401 selected dose and placebo). No new patients will be randomised to SENS-401 non-selected dose.

The SENS-401 dose to be tested in Part 2 will be identified by the DMC using the unblinded data from Part 1. The rationale will be based on the benefit/risk at each dose. PTA at 28 days will be considered for efficacy. This committee will be independent from the sponsor. The final dose and sample size will be submitted for approval to competent authorities prior to the pivotal part start.

Each part will be analysed separately. Part 1 will be fully analyzed when all patients (n= 111) have completed the study. Part 2 efficacy analysis will be based on data from all patients who have entered into Part 2 and have been randomised to either placebo or the selected active dose (n=190).

### 7.3 Independent Review Procedures

An external data monitoring committee (DMC), consisting of two or more physicians and a statistician, independent from the sponsor and the monitoring team will be set up to review the safety of the product throughout the conduct of the study, as well as the efficacy (see section 12.8.1).

During Part 1, two interim efficacy looks are planned. They will be performed by an independent statistician dedicated to the efficacy analyses according to a Group Sequential Test (GST) design. Each of these interim looks will lead to an automatically generated recommendation to the sponsor of continuing the study or of discontinuing the study for efficacy or futility respectively.

The committee will review the results and will provide further recommendation to the sponsor for stopping Part 1 for efficacy, futility or continuing as planned until the next look or the final analysis of Part 1.. No information about these results will be communicated to investigators and the International Coordinating Investigators until the study is completed or discontinued.

The committee will be responsible for selecting the active dose to be tested in Part 2. The committee will be provided with the unblinded efficacy and safety data on the primary endpoint when 111 patients randomised to Part 1 have completed the 4-week treatment. The DMC will review the safety information together with the efficacy data to decide on the benefit/risk and recommend appropriate measures if needed. The DMC may also recommend to modify the sample size of the Part 2 study.

### 7.4 Study diagram

As soon as eligibility of the patient is confirmed, the investigator will dispense to the subject the study drug that is to be taken immediately after all baseline assessments are performed.

#### **Part 1**

The study diagram is presented in **Erreur ! Source du renvoi introuvable..**

[figure not shown]

Figure 2: Part 1 and Part 2 (until dose selection) Study Diagram

Until the dose selection, the study diagram will be similar to Part 1 (see **Erreur ! Source du renvoi introuvable.**).

### Part 2

After the dose selection, the study diagram is as follows (see Figure 3):

[figure not shown]

Figure 3: Part 2 (after dose selection) Study diagram

### 7.5 Number of subjects and duration of study participation

It is planned to enroll a total of 301 or less patients in the study.

Part 1: 111 patients will be enrolled (37 in the placebo arm; 37 in SENS-401 29mg arm, 37 in SENS-401 43.5mg arm)

Part 2: 190 patients will be enrolled (95 in the placebo arm; 95 in selected-dose SENS-401 arm; and approximately 10 in the non-selected dose SENS-401 arm)

Each patient's participation in the study will be 12 weeks:

- 1 to 4 days screening
- 28 days of double blind treatment
- A follow up with no investigational product until 84 Days after inclusion.

#### 7.6 Determination of end of clinical trial (all patients)

The first part of the study will be considered complete when all patients randomised in Part 1 have completed all the scheduled procedures as described in the flow chart ([Section 4](#)). Any withdrawal from treatment during the 28-day treatment period will be considered as treatment discontinuation.

The end of trial will be considered after the last subject last visit.

## 8 INCLUSION AND EXCLUSION CRITERIA

Patients will be included if they are presenting with unilateral sudden sensorineural hearing loss (noise induced or idiopathic) and have met all the following inclusion criteria and no exclusion criteria:

### 8.1 Inclusion criteria

1. Male or female
2. Aged at least 18 years old
3. Patients with unilateral idiopathic sudden sensorineural hearing loss or unilateral/bilateral acute acoustic trauma leading to SSNHL defined by both:
  - 3.1. At least 1 hearing threshold of 50 dB or more among the 3 most affected contiguous frequencies on pure tone audiometric air conduction testing performed 24 hours or less prior to first study treatment), and
  - 3.2. Mean hearing loss of 30 dB or more, averaged across the 3 most affected contiguous frequencies on pure tone audiometric air conduction testing (PTA: Pure Tone Average) performed 24 hours or less prior to first study treatment), compared with the unaffected contralateral ear or reference values from a pre-existing audiogram (dated less than 2 years)
4. Patients with sudden hearing loss with onset within 96 hours prior to prior to first study drug intake.
5. Females must meet 1 of the following: Postmenopausal defined as 12 consecutive months with no menses without an alternative medical cause or Surgically sterile or Abstinent or Practicing **highly** effective birth control (must agree to use 2 forms of contraception [1 of which must be a barrier method]) (Appendix 4) and willing to continue to use **highly** effective contraception for the duration of study participation and for 30 days after the final dose of study drug). Women of childbearing potential must have a negative pregnancy test at screening before the first dose of study drug is taken. Women of childbearing potential are defined as any female who has experienced menarche and who is not permanently sterile or postmenopausal.
6. Male subjects and their female partner(s) must agree to use highly effective contraception (must agree to use 2 forms of contraception [1 of which must be a barrier method]) (Appendix 4) for the duration of study participation and for 90 days after the final dose of study drug.
7. Signed and dated written informed consent.

### 8.2 Exclusion criteria

Patients who have met all the above inclusion criteria listed in Section 8.1 will be screened for the following exclusion criteria:

1. Bilateral idiopathic hearing loss
2. Fluctuating hearing loss
3. History of asymmetric hearing (>20dB difference between ears) to the best knowledge of the patient
4. Severe hearing loss (>90 dB) associated with unilateral (ipsilateral) complete vestibular loss.

5. History of Ménière's disease, autoimmune hearing loss, radiation-induced hearing loss, acoustic neuroma (schwannoma)
6. Previous SSNHL in the affected ear within the past 6 weeks
7. History of otosclerosis, suspected perilymph fistula or membrane rupture, suspected retro-cochlear lesion, barotrauma
8. Congenital or hereditary hearing loss
9. History of severe head or neck trauma
10. Complete loss of peripheral vestibular function on the affected side
11. Any drug-based therapy for inner ear hearing loss that is ongoing or was performed over the past 6 weeks (except oral corticosteroids)
12. Any ongoing or planned concomitant medication for the treatment of tinnitus until 6 weeks after administration.
13. Any therapy known as ototoxic (e.g. aminoglycosides, cisplatin, loop diuretics, quinine etc.) at the current time or in the past 6 months prior to study inclusion.
14. Air-bone gap of greater than 20 dB in 3 contiguous frequencies
15. Acute chronic otitis media or otitis externa terminated less than 7 days prior to randomisation.
16. History of chronic inflammatory or suppurative ear disease or cholesteatoma
17. Prior ear surgery of any kind (except ventilating tubes), or cochlear implants
18. Patients with moderate to severe renal impairment defined by a creatinine clearance  $\leq$  60 ml/min (calculated with the Cockcroft-Gault formula for patients  $<65$  years old and with CKD-EPI creatinine equation or with MDRD equation for patients  $\geq 65$  years old)
19. Treatment with triptans in the 24 hours before inclusion.
20. History of drug abuse or alcoholism within the last 2 years
21. Known or suspected ongoing active infection of HIV, Hepatitis B or C, or herpes zoster
22. Known history of, or concomitant severe hepatic, gastrointestinal, cardiovascular, respiratory, neurological (except vertigo or tinnitus), hematological, renal, dermatological or psychiatric disease or substance abuse or any condition that, in the opinion of the Investigator might interfere with the evaluation of study treatment or warrant exclusion (see list of discontinuation criteria, section 11.3.2)
23. Patients who, in the opinion of the investigator, have any clinically relevant findings that warrant exclusion. Examples of clinically relevant problems include, but are not limited to, serious non-malignancy-associated medical conditions that may be expected to limit life expectancy or significantly increase the risk of SAEs and any condition, psychiatric, substance abuse, or otherwise, that, in the opinion of the Investigator, would preclude informed consent, consistent follow-up, or compliance with any aspect of the study
24. Neurological disorders including stroke, demyelinating disease, brain stem or cerebellar dysfunction within the last 3 months. (In case of possible stroke of the brainstem or cerebellum, or demyelinating disease the diagnosis should have been excluded by a MRI performed in the past 48 hours)

25. Known hypersensitivity, allergy or intolerance to the study medication or any history of severe abnormal drug reaction
26. Pregnant or breast-feeding
27. Mentally unable to understand the nature, objectives and possible consequences of the trial, or refusing its constraints
28. Treatment with any investigational agent within 4 weeks prior to randomisation or 5 half-lives of the investigational drug (whichever is longer)
29. Prior participation in a clinical trial with SENS-401 or any past treatment with azasetron.
30. Patient is the investigator or any sub-Investigator, research assistant, pharmacist, study coordinator, other staff or relative thereof directly involved in the conduct of the protocol.
31. Patients with either a history of significant arrhythmia, or a history of conditions known to increase the proarrhythmic risk (e.g., congestive heart failure, long QT Syndrome, hypokalemia etc...).

## 9 TREATMENT

### 9.1 Investigational Product

SENS-401 14.5 mg tablets (10 mg free base), with a matching placebo

Doses in Part 1:

- 29 mg dose group: 2 tablets of 14.5 mg SENS-401 and 1 tablet of matching placebo twice daily (morning and evening), oral route
- 43.5 mg dose group: 3 tablets of 14.5 mg SENS-401 twice daily (morning and evening), oral route
- Placebo group: 3 matching placebo tablets twice daily (morning and evening), oral route

Doses in Part 2:

- 29 mg dose group: 2 tablets of 14.5 mg SENS-401 and 1 tablet of matching placebo, twice daily (morning and evening), oral route. Depending upon the final dose selected, if this dose is the non-selected dose, it will be stopped immediately after the decision is taken
- 43.5 mg dose group or 3 tablets of 14.5 mg SENS-401, twice daily (morning and evening), oral route. Depending upon the final dose selected, if this dose is the non-selected dose, it will be stopped immediately after the decision is taken
- Placebo group: 3 matching placebo tablets twice daily (morning and evening), oral route

Duration: Given for 28 days.

Administration Route: The tablets must be swallowed with water

### 9.2 Non-Investigational Product

There is no medical treatment recommended by the medical societies. However, all patients will receive concomitantly oral corticosteroids, unless contra-indicated, which is standard of care treatment. The type and dose will be at the discretion of the investigator and recorded in the e-CRF. Administration of intratympanic treatments, including corticosteroids, is not authorized until day 14. A rescue treatment with intratympanic corticosteroids may be proposed from day 14 in case of non-response.

### 9.3 Description of blinding methods

The SENS-401 and placebo tablet are identical.

Two lists of randomisation using a 1:1:1 randomisation ratio will be generated for the whole study, one for the French sites involved in the ancillary study and one for all the other sites globally, including French sites not participating in the ancillary study.

During Part 1, the 3 treatment arms will be used. During Part 2 the 3 treatment arms will continue to be allocated until one active dose is selected. After dose selection, only the placebo and the selected active dose will continue to be allocated.

The lists of randomisation will be generated centrally, and the investigator, the sponsor study team, the CRO or subjects will be blinded to the Investigational drug administration. The lists of randomisation will be stratified by the duration of the disease at baseline ( $\geq 24$  hours or  $< 24$  hours) and oral corticosteroids intake at baseline (no, yes).

Pharmacokinetic parameters that could potentially unblind the study team will not be disclosed during the conduct of the study.

Investigators will have no access to the randomisation code except under special circumstances. In case of an emergency, when knowledge of the randomisation status is deemed necessary for the medical care of the patient, the randomisation code can be unblinded for a specific patient (see section 11.3.4).

#### 9.4 Randomisation process

The randomisation will be managed centrally using an interactive web response system (IWRS). The IWRS allocates a treatment number to the patient according to the relevant randomisation list (non ancillary study sites or ancillary study sites), and the further stratification on the duration of the disease ( $\geq 24$  hours or  $< 24$  hours), and oral corticosteroids intake at baseline (no, yes). During the course of the study, one of the two active treatment arms may be disabled (dose dropped after decision of Part 2).

A patient will be considered randomised when the IWRS has given the treatment number to be allocated.

All randomised subjects (Day 1) will receive either SENS 29 mg, or SENS 43.5 mg or Placebo treatment at the study site according to the IWRS allocation.

The treatment will be then self-administered twice daily to all patients for 28 days.

A patient cannot be randomised more than once during the study.

#### 9.5 Packaging and labeling

SENS-401 and matching placebo will be inserted in bottles with a child resistant cap. The bottles are packaged and labeled into a sealed clinical pack that includes 3 bottles including 30 tablets each of the investigational product or placebo for a 14-day administration including 1 additional day (rescue tablets). Twice daily, each patient will take 3 tablets (one tablet from each of the 3 bottles) included in one assigned pack. Each patient will receive 2 clinical packs (inserted into a final pack) according to the randomisation lists. During the 28-day treatment period, in exceptional case of any bottle being lost, the IWRS can allocate a replacement treatment number to a patient. The first dose to be administered at the study site will be taken out from one of the clinical packs that will be dispensed to the patient on Day 1 (visit 2), to be taken home. The content of the labeling is in accordance with the local regulatory specifications and requirements.

## 9.6 Accountability and compliance

The date and time of the first intake will be recorded on the eCRF.

The patient will be instructed to return all used and unused investigational kits at every on-site visit. He/she will be provided a diary to record the intake of IP (number of tablets, date and time). The investigator or designee will count the returned tablets and complete the corresponding e-CRF.

The type and dose of corticosteroids will be recorded on the eCRF. The patient will record the intake of corticosteroid in the diary. Corticosteroids intake will be also recorded on the e-CRF, based on the patient's information.

## 9.7 Storage conditions

SENS-401 and matching placebo should be stored in a secure location with restricted access to authorized study staff at room temperature as described on the investigational product labeling. The investigational product is under the responsibility of the study site, and should be handled according to local regulation, and label specifications.

Patients should be warned to store the treatment according to the labeling and out of reach of children. They will be warned not to take the tablets out of the bottles in advance. They will be requested to return the bottles with the remaining tablets at the following on site visit.

## 9.8 Responsibilities

The Investigator, the Hospital Pharmacist, or any other staff member allowed to store and dispense Investigational Product will be responsible for ensuring that the investigational product used in the study is securely maintained as specified by the Sponsor and in accordance with the applicable regulatory requirements.

The investigational product should not be supplied to any non-authorized person and should not be used other than as described in this protocol.

## 9.9 Management of treatment at the end of the study

All partially used or unused investigational product (IP) will be returned to Sensorion or designee at the end of the study, as described in the shipment procedure. The site should not destroy any treatment without a specific written information from the sponsor.

In case of destruction of the IP, the information about date and location of destruction, sort and amount of the IP, reason and contact details of the person who destroyed the IP should be recorded.

## 9.10 Concomitant treatment

### 9.10.1 Background therapy

Corticosteroids by oral route (including but not limited to prednisone, methyl prednisolone, dexamethasone) are usually considered as the standard of care (Appendix 6). The guidelines published by the AAO-HNS recommend prednisone for patients with SSNHL within 2 weeks after the diagnosis, with a recommended dose of Prednisone 1 mg/kg/day (max: 60 mg/day), or Methylprednisolone 48 mg/d or Dexamethasone 10 mg/d given as a single dose for 7-14 days, then taper over similar time period. Since there is no harmonization on this clinical practice,

---

each site will be requested to pre-specify the type and dosage regimen of oral corticosteroid that will be given to patients as standard of care. Unless contra-indicated, the pre-specified oral corticosteroids will be prescribed to all patients at a given site. The time, dose and route of administration will be recorded on the e-CRF. The randomisation will be stratified according to the corticosteroid intake. Compliance of the corticosteroids intake will be assessed by the investigator at every on-site visit from the patient diary. Any contra-indication will be recorded on the e-CRF at the sites.

#### **9.10.2 Authorized concomitant medication**

Any drugs other than those listed below are permitted, if considered necessary for the subject and administered at a stable dose, at the discretion of the Investigator.

Any new concomitant medication (started prior to the study and/or prescribed during the study) should be recorded on the case report form. In case of treatment given for any untoward event, an adverse event form should be completed on the e-CRF.

#### **9.10.3 Not permitted concomitant medication**

The medications listed below are not permitted, unless in exceptional circumstances (see below rescue medication):

Corticosteroids by intratympanic route (including but not limited to prednisone, methyl prednisolone, dexamethasone) is not permitted except from D14 where they can be given as rescue medication (see criteria in section 9.9.3.)

Other intratympanic treatments

Hyperbaric oxygen

Antivirals, vasodilators, vasoactive substances, or antioxidants. In case of chronic treatment for reasons other than inner ear diseases, these agents can be continued but the dose regimen must not be modified until the end of the treatment period

Any investigational drug,

Any ototoxic treatment (e.g. aminoglycosides, cisplatin, loop diuretics, quinine etc.)

Initiation of antidepressant treatment containing serotonergic agents within the previous 24 hours (see non-exhaustive list of serotonergic agents in Appendix 7) due to the risk of serotonergic syndrome.

Substrates of BCRP and transporter (see non-exhaustive list in Appendix 8)

5 HT3 antagonists (ondansetron, tropisetron, palonosetron, granisetron etc..) and calcineurin inhibitors (cyclosporine, tacrolimus, azasetron)

Any additional medication aiming at treating SSNHL must be discussed with the monitoring team.

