### 5.3.3 SENS-401 toxicology

SENS-401 has been administered to rats and dogs for 1 month. The safety was good with a NOAEL dose > 25 mg/kg/day (free-base equivalent) in the dog, corresponding to Cmax >3200ng/mL and, AUClast >10800ng.h/mL. In the rat, the NOAEL was >157 mg/kg/day (free-base equivalent), corresponding to a Cmax > 9800 ng/mL, AUClast > 80500 ng.h/mL. In a telemetry study, SENS-401 was shown to slightly reduce blood pressure resulting in modest dose independent increases in heart rate and then QT interval (<30ms) with no relationship with dose or concentrations. No target organ has been identified.

As SENS-401 is a substrate of MDR1 and BCRP transporters, drugs that are inhibitors of these are listed as prohibited. In *in vitro* experiments using recombinant enzymes, some CYP2B6 inhibition was observed at 25 μM (approximately 37 %) which did not increase at 100 μM (approximately 24 %). This level of inhibition at a very high concentration is unlikely to cause any interactions clinically. Therefore, no restrictions are proposed in the protocol.

Patients will be advised to avoid skin exposure to strong sunlight and to wear sunglasses in bright sunlight for the duration of the study and for 1 week after the last dose.

No specific safety concern was identified from the 3-month oral toxicity studies, and reprotoxicology studies performed with the racemic mixture. Genotoxicity studies were negative.

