### Appendix 8: Clinical inhibitors for transporters

**Examples of clinical inhibitors for transporters (for use in clinical DDI studies and drug labeling)  
 (9/26/2016)**

(<https://www.fda.gov/Drugs/DevelopmentApprovalProcess/DevelopmentResources/DrugInteractionLabeling/ucm093664.htm#table5-2>)

Transporter	Gene	Inhibitor
P-gp	ABCB1	amiodarone, carvedilol, clarithromycin, dronedarone, itraconazole, lapatinib, lopinavir and ritonavir, propafenone, quinidine, ranolazine, ritonavir, saquinavir and ritonavir, telaprevir, tipranavir and ritonavir, verapamil
BCRP	ABCG2	curcumin, cyclosporine A, eltrombopag
OATP1B1, OATP1B3	SLCO1B1 , SLCO1B3	atazanavir and ritonavir, clarithromycin, cyclosporine, erythromycin, gemfibrozil, lopinavir and ritonavir, rifampin (single dose), simeprevir
OAT1, OAT3	SLC22A6 , SLC22A8	p-aminohippuric acid (PAH), probenecid, teriflunomide
MATE1, MATE2-K	SLC47A1 , SLC47A2	cimetidine, dolutegravir, isavuconazole, ranolazine, trimethoprim, vandetanib

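### Protocol 9.10.3 bars BCRP substrates where 5.3.3 and Appendix 8 concern inhibitors, so read literally the rule misfires for some drugs that Appendix 8 does not name

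*Protocol*

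**What the plan says.** Four places in the protocol bear on this; the SAP does not address transporter drugs.

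- **Section 5.3.3 (toxicology)** gives the rule and its reason: "As SENS-401 is a substrate of MDR1 and BCRP transporters, drugs that are inhibitors of these are listed as prohibited".
- **Section 9.10.3 (not permitted concomitant medication)**, the list a site works from, reads: "Substrates of BCRP and transporter (see non-exhaustive list in Appendix 8".
- **Appendix 8** is introduced as "Examples of clinical inhibitors for transporters (for use in clinical DDI studies and drug labeling". Its drug column is headed Inhibitor and it contains no substrate list. The BCRP row reads "curcumin, cyclosporine A, eltrombopag".
- **Section 9.10.2 (authorized concomitant medication)** sets the default. Drugs outside the prohibited list "are permitted, if considered necessary for the subject and administered at a stable dose, at the discretion of the Investigator".

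No exclusion criterion in section 8.2 mentions transporter inhibitors, and no other text in the protocol corrects the word used in 9.10.3.

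**The concern.** A substrate is carried by a transporter; an inhibitor blocks it. If SENS-401 is the substrate, co-medication that blocks MDR1 or BCRP could alter its exposure, and that is the reason 5.3.3 gives for the restriction. Barring other BCRP substrates would make sense if SENS-401 itself inhibited BCRP, which the protocol nowhere says. The operative line therefore names a class that does not match the stated reason.

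Two things are at stake. First, a site following 9.10.3 literally could accept an inhibitor that 5.3.3 means to keep out, while a site following 5.3.3 would refuse the same drug. About 50 centers are planned, so different readings are plausible. Second, the same co-medication could be logged as a deviation at one site and not at another, and major deviations feed the per-protocol set (SAP 6.1.2) used in the first sensitivity analysis (SAP 6.12.3).

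**Working it through.** No sample size, power or alpha figure is involved. The check sets the texts side by side.

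**Step 1: named drugs.** Appendix 8 has 15 entries in the P-gp row and 3 in the BCRP row, 15 + 3 = 18 in all. The cross-reference in 9.10.3 catches all of them whatever the class word says. For BCRP, the one transporter that the line names, cyclosporine is also barred elsewhere in 9.10.3 as a calcineurin inhibitor. The list therefore adds 3 − 1 = 2 drugs.

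**Step 2: unnamed drugs.** Section 9.10.3 calls the list non-exhaustive and Appendix 8 calls its entries examples. For any other drug the class word decides, with 9.10.2 as the default:

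| Drug not named in Appendix 8 | 9.10.3 read literally | 5.3.3 | Agree? |
|---|---|---|---|
| Inhibits MDR1 or BCRP, not a BCRP substrate | Not barred by this line; 9.10.2 applies | To be prohibited | No |
| BCRP substrate, inhibits neither | Barred | No reason to bar | No |
| BCRP substrate that also inhibits MDR1 or BCRP | Barred | To be prohibited | Yes, by coincidence |
| None of these | Not barred by this line | Not restricted | Yes |

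The first row holds only where no other line of 9.10.3 bars the drug. Antivirals (apart from chronic use for reasons other than inner ear disease), ototoxic treatments, 5-HT3 antagonists and calcineurin inhibitors are barred separately.

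**Step 3: the missing word.** The line seems to have lost a word before its last noun, and MDR1 does not appear in it. The loss may come from text extraction, so it is not counted as an error. If the lost word is MDR1, the line bars substrates of both transporters. The first row then shrinks to inhibitors that are substrates of neither, and the second row grows. The mismatch of class remains.

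**Step 4: scope of the cross-reference.** Appendix 8 also has rows for OATP, OAT and MATE inhibitors. Section 5.3.3 gives no reason to restrict these, yet a reference to the whole appendix brings them in.

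**The case against.** The strongest reply is that the intended class is plain. The appendix cited in the same line contains only inhibitors, the line is visibly garbled, and 5.3.3 states the rule. A careful investigator would read inhibitors. This has force, and it is the main reason the point is minor. It does not remove the point, because the enforceable list should not need a background section to reverse its meaning.

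Other replies also stand in part:

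- **Some likely users of inhibitors never enter.** Section 8.2 excludes "Known or suspected ongoing active infection of HIV, Hepatitis B or C, or herpes zoster" (no. 21), severe disease (no. 22) and "Patients with either a history of significant arrhythmia, or a history of conditions known to increase the proarrhythmic risk" (no. 31).
- **There is monitoring.** Triplicate ECGs are taken at baseline and Days 7, 14 and 28 (10.2.4), confirmed QTc above 500 ms is a withdrawal criterion (11.3.2), and the DMC sees the ECG database (12.8.1). Drug levels are a weaker check. They are sampled only at Days 14 and 28 (10.3), and section 9.3 adds: "Pharmacokinetic parameters that could potentially unblind the study team will not be disclosed during the conduct of the study".
- **Deviations are reviewed centrally.** The sponsor assesses any deviation (14.7), and all are assessed case by case before database lock (SAP 6.1.2). This limits, but does not prevent, uneven logging at sites.
- **A bar on substrates might be intended.** Section 5.3.4 refers to the Investigator Brochure for all available information on SENS-401, and it is not among the documents. This cannot be settled here, so the fix asks the sponsor to confirm.
- **If 5.3.3 already binds sites, the harm is small; if it does not, the correction adds a restriction in practice.** Both halves are fair. The protocol does not say which section governs, and that ambiguity is the defect.

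A reader might go further and infer that the protocol lets in MDR1 and BCRP inhibitors generally. It does not: the named ones stay barred, and an unlisted drug that is both inhibitor and BCRP substrate is barred too.

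**Conclusion.** The inconsistency is real and sits in current text. Read literally, 9.10.3 fails to bar an unlisted MDR1 or BCRP inhibitor that is not a BCRP substrate, and it bars an unlisted BCRP substrate without a stated reason.

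Severity is minor. The documents give no count of patients on such drugs and no clinical data on SENS-401 with a transporter inhibitor; the number affected is probably small. The conclusion assumes that 5.3.3 states the sponsor's intention and that some sites will take 9.10.3 at its word.

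Three stronger readings are not supported:

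- **That the efficacy comparison is compromised.** The primary analysis is by intention to treat, and nothing in the sample size, power or type I error depends on this line.
- **That patients are at a quantifiable risk.** Animal exposure margins and the number of patients still to be enrolled may look relevant, but neither measures how many patients take an affected drug or what that does to SENS-401 levels. Current enrolment is not stated, so urgency cannot be argued from it either.
- **That barring substrates was a design choice.** No rationale for it appears, and the two related texts point the other way. It reads as a drafting error.

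**What to change.** Change the line in 9.10.3 to: *Inhibitors of MDR1 (P-gp) and BCRP transporters (see the P-gp and BCRP rows of the non-exhaustive list in Appendix 8)*. Naming both MDR1 and P-gp links the term in 5.3.3 to the row label in the appendix. Limiting the reference to two rows takes the OATP, OAT and MATE inhibitors out of scope.

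Before the substrate wording goes, the sponsor should confirm that no separate bar on BCRP substrates was intended. If one was, keep it as its own line with its reason.

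Send sites a short clarification now, citing 5.3.3, to say that inhibitors are the class to keep out. It restates existing protocol text. It should not lift the bar on substrates, which waits for the confirmed text change. Make that change in the next amendment, at the latest the one that section 14.4 requires before Part 2.

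The cost is one line of text, one sponsor query and one site notice. Under section 14.9 a non-substantial change is filed and notified; a substantial one needs prior approval and can travel with the amendment already due. A site that has worked from 9.10.3 alone will see a new restriction on unlisted inhibitors. Measured against 5.3.3, nothing is added.
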